Laboratory Tests (includes blood and urine samples)	FU1 -yes FU2 - if toxicities are present		See Section 9.4.1 for additional details on tests required. 
 • CBC w/differential, PT/INR, and PTT • Chemistry panel (includes AST, ALT, total bilirubin, ALP, LDH, creatinine, BUN, glucose, albumin, Na, K, Cl, Ca, P, Mg, amylase, lipase) • Thyroid panel (includes TSH with reflexive free T3 and free T4) • Urine protein and urine creatinine (for UPCR, preferred) or urine dipstick for protein
Pregnancy Test	X		Serum or Urine. WOCBP only.
Efficacy Assessments			
Tumor Assessments	First tumor assessment post-baseline should be performed Week 12 (± 7 days) following randomization. Use same imaging method as was used at baseline.		Participants who discontinue study treatment without radiographic progression, confirmed by BICR, will continue tumor assessments according to the protocol specified schedule, even if new anti-tumor therapy has been initiated in the Follow-Up phase, until radiographic

- ^a Participants must be followed for at least 100 days after last dose of study treatment. Follow-up visit #1 (FU1) should occur 30 days from the last dose (+/- 7) days or can be performed on the date of discontinuation if that date is greater than 42 days from last dose. Follow-up visit #2 (FU2) occurs approximately 100 days (+/- 7 days) from last dose of study drug. Both Follow Up visits should be conducted in person.
- ^b Survival Follow-up visits to occur every 3 months from Follow-up Visit #2. Survival visits may be conducted in person or by telephone. BMS may request that survival data be collected on all treated participants outside of the 3 month specified window. At the time of this request, each participant will be contacted to determine their survival status unless the participant has withdrawn consent for all contact.

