Laboratory Tests (includes blood and urine samples)	X	See Section 9.4.1 for additional details on tests required. To be completed locally at each site. Must be performed within 14 days prior to randomization. 
 • CBC w/differential • PT/INR, PTT • Chemistry panel (includes AST, ALT, total bilirubin, ALP, LDH, creatinine, BUN, glucose, albumin, Na, K, Cl, Ca (also corrected), P, Mg, amylase, lipase) • Thyroid panel (includes TSH with free T3 and free T4) • Hepatitis B/C (HBVsAg, HCV antibody or HCV RNA) • HIV if mandated locally (sites in Germany, see Appendix 12) • Urine protein and urine creatinine (for urine protein/creatinine ratio [UPCR]). If UPCR \geq 1.0, obtain 24 hour urine protein.
Pregnancy Test	X	WOCBP only. Serum or urine pregnancy test (minimum sensitivity 25 IU/L or equivalent units of HCG) to be done at screening visit and within 24 hours of first dose of study therapy.
Follicle Stimulating Hormone (FSH)	X	For women under the age of 55 years to confirm menopause as needed.
Efficacy Assessments		
Baseline Tumor Assessments	X	CT/MRI of the chest, abdomen, pelvis, brain, and all known sites of disease, performed within 28 days prior to randomization. All scans need to be submitted for blinded independent central review (BICR). See Section 9.1 .

Abbreviations: For abbreviations on lab tests refer back to [Section 9.4.1](#).

^a Some of the assessments referred to in this section may not be captured as data in the eCRF. They are intended to be used as safety monitoring by the treating physician. Additional testing or assessments may be performed as clinically necessary or where required by institutional or local regulations.

Table 2-2: On Treatment Procedural Outline for Arm A Nivolumab Combined with Cabozantinib, Doublet (CA2099ER)

Procedure	Cycle 1, Day 1 Cycle=2 wks	C2 and subsequent visits ^a Each Cycle=2 wks	Notes
Safety Assessments			
Targeted Physical Examination, Vital Signs, Performance Status	X	X	Weight, BP, HR, RR, temperature, and Karnofsky Performance Status (KPS) (Appendix 7). Performance Status to be performed within 72 hours prior to dosing.
Assessment of Signs and Symptoms	X	X	

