Adverse Events and Serious Adverse Events Assessment	X	X	Record at each visit. Participants will be followed for drug-related toxicities until these toxicities resolve, return to baseline, or are deemed irreversible. All adverse events will be documented for a minimum of 100 days after last dose (Appendix 3).
██████████	█	█	██████████
Electrocardiogram (ECG)	X	X (See notes)	Fridericia corrected QT (QTcF) required. Only for Cycles 1, 4, 7, then every 6 cycles (ie, Cycles 13, 19, 25, etc). If any time there is an increase in QTcF interval to an absolute value > 500 msec, 2 additional ECGs must be performed each with intervals approximately 3 minutes apart.
Laboratory Tests (includes blood and urine samples)	X	X (See notes)	See 9.4.1 for additional details on tests required. Laboratory tests do not need to be repeated at C1D1 if performed within 14 days prior to first dose. After C1D1, within 72 hours prior to dosing: 
 • CBC w/differential at every cycle • Chemistry panel at every cycle (includes AST, ALT, total bilirubin, ALP, LDH, creatinine, BUN, glucose, albumin, Na, K, Cl, Ca, P, Mg) • Amylase and lipase to be done for Cycles, 1, 2, 4, 5, 7, and then every 3 cycles (ie, Cycles 10, 13, 16, etc) • Thyroid panel (includes TSH with reflexive free T3 and free T4) for Cycles 1, 2, 4, 5, 7, and then every 3 cycles (ie, Cycles 10, 13, 16, etc) • Urine protein and urine creatinine (for UPCR, preferred) or urine dipstick for protein every 3 cycles (ie, Cycles 1, 4, 7, 10, etc).

Table 2-2: On Treatment Procedural Outline for Arm A Nivolumab Combined with Cabozantinib, Doublet (CA2099ER)

Procedure	Cycle 1, Day 1 Cycle=2 wks	C2 and subsequent visits ^a Each Cycle=2 wks	Notes
Pregnancy Test	X	X	Within 24 hours prior to the initial administration of study drug, then every 4 weeks ± 7 days. Serum or Urine. WOCBP only.
Efficacy Assessments			

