Abbreviations: C=cycle; D=day; wks= weeks. For abbreviations on lab tests refer back to [Section 9.4.1](#).

Notes: Some of the assessments referred to in this section may not be captured as data in the eCRF. They are intended to be used as safety monitoring by the treating physician. Additional testing or assessments may be performed as clinically necessary or where required by institutional or local regulations.

^a If a dose is delayed, the procedures scheduled for that same timepoint should also be delayed to coincide with when that timepoint’s dosing actually occurs.

Table 2-4: On Treatment Procedural Outline for Arm C Sunitinib (CA2099ER)

Procedure	Cycle 1 Each Cycle=6wks		Cycle 2 ^a Each Cycle=6 wks		C3 and Subsequent visits ^a Each Cycle=6 wks		Notes
	Day 1	Day 22 (+/- 3 days)	Day 1	Day 22 (+/- 3 days)	Day 1	Day 22 (+/- 3 days)	
Safety Assessments							
Targeted Physical Examination, Vital Signs, Performance Status	X		X		X		Weight, BP, HR, RR, temperature, and Karnofsky Performance Status (KPS) (Appendix 7). Performance Status to be performed within 72 hours prior to dosing.
Assessment of Signs and Symptoms	X	X	X	X	X	X	
Adverse Events and Serious Adverse Events Assessment	X	X	X	X	X	X	Record at each visit. Participants will be followed for drug-related toxicities until these toxicities resolve, return to baseline, or are deemed irreversible. All adverse events will be documented for a minimum of 100 days after last dose (Appendix 3).
[REDACTED]	■	■	■	■	■	■	[REDACTED]
Electrocardiogram (ECG)	X		X		X (See notes)		Fridericia corrected QT (QTcF) required. Only Cycles 1, 2, and 3, then every 2 cycles (ie, Cycles 5, 7, 9, etc). If any time there is an increase in QTcF interval to an absolute value > 500 msec, 2 additional ECGs must be performed each with intervals approximately 3 minutes apart.
Laboratory Tests (includes blood and urine samples)	X	X (See notes)	X	X (See notes)	X	X (See notes)	See Section 9.4.1 for additional details on tests required. Laboratory tests do not need to be repeated at C1D1 if performed within 14 days prior to first dose. After C1D1, within 72 hours prior to specified dosing day: 
 CBC w/differential on Day 1 and Day 22 (+/- 3 days) of each cycle

Table 2-4: On Treatment Procedural Outline for Arm C Sunitinib (CA2099ER)

Procedure	Cycle 1 Each Cycle=6wks		Cycle 2 ^a Each Cycle=6 wks		C3 and Subsequent visits ^a Each Cycle=6 wks		Notes

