	Day 1	Day 22 (+/- 3 days)	Day 1	Day 22 (+/- 3 days)	Day 1	Day 22 (+/- 3 days)	
							
 Chemistry panel on Day 1 and Day 22 (+/- 3 days) of every cycle (includes AST, ALT, total bilirubin, ALP, LDH, creatinine, BUN, glucose, albumin, Na, K, Cl, Ca, P, Mg) Amylase and lipase on Day 1 and Day 22 (+/- 3 days) of Cycle 1 and 2, then on Day 1 of Cycle 3 and all subsequent cycles. Thyroid panel (includes TSH with reflexive free T3 and free T4) on Day 1 and Day 22 (+/- 3 days) of Cycle 1 and 2, then on Day 1 of Cycle 3 and all subsequent cycles. Urine protein and urine creatinine (for UPCr, preferred) or urine dipstick for protein on Day 1 of every cycle
Pregnancy Test	X	X	X	X	X	X	Within 24 hours prior to the initial administration of study drug, then every 4 weeks ± 7 days. Serum or Urine. WOCBP only.
Efficacy Assessments							
Tumor Assessments	
First tumor assessment post-baseline should be performed Week 12 (± 7 days) following randomization. Use same imaging method as was used at baseline.
 
Subsequent tumor assessments should occur at every 6 weeks (± 7 days) until Week 60, then every 12 weeks (± 14 days) until radiographic progression, assessed by the investigator and confirmed by the BICR.
					
CT/MRI of the chest, abdomen, pelvis, and all known sites of disease.
 
Tumor assessments should be performed at the specified time points regardless of dosing delays. See Section 9.1 for additional details.
 
Treatment Beyond Progression
 
A radiographic assessment/ scan should be performed within 6 weeks of initial investigator-assessed
	

Table 2-4: On Treatment Procedural Outline for Arm C Sunitinib (CA2099ER)

Procedure	Cycle 1 Each Cycle=6wks		Cycle 2 ^a Each Cycle=6 wks		C3 and Subsequent visits ^a Each Cycle=6 wks		Notes
	Day 1	Day 22 (+/- 3 days)	Day 1	Day 22 (+/- 3 days)	Day 1	Day 22 (+/- 3 days)	
							progression. Refer to Section 8.1.4 for tumor assessment associated with Treatment beyond progression.
[REDACTED]							
[REDACTED]	■						[REDACTED]
[REDACTED]	■		■				[REDACTED]
[REDACTED]	■		■				[REDACTED]
[REDACTED]	■						[REDACTED]
[REDACTED]	■		■				[REDACTED]
[REDACTED]	[REDACTED]						[REDACTED]
[REDACTED]	[REDACTED]						[REDACTED]

Table 2-4: On Treatment Procedural Outline for Arm C Sunitinib (CA2099ER)

Procedure	Cycle 1 Each Cycle=6wks		Cycle 2 ^a Each Cycle=6 wks		C3 and Subsequent visits ^a Each Cycle=6 wks		Notes

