7.1.2 Laboratory Tests

Clinical laboratory parameters (hematology, serum chemistry and electrolytes) will be evaluated.

Laboratory tests will be graded using the NCI Common Terminology Criteria, and the most recent version of the criteria at the time of the database lock will be used.

Clinical laboratory data will be first analyzed using International System of Units (SI).

Analyses will be repeated using US conventional units.

In the laboratory summary tables, unless otherwise specified, subjects will be counted only once for each lab parameter according to their worst on treatment CTC grade (worst being the highest

CTC grade). The laboratory tables and listings will be sorted by laboratory category, laboratory subcategory and laboratory test code sequence number.

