7.6.10.2 Serum Chemistry

The following will be summarized by treatment group as worst CTC grade on-treatment per subject and as shift table of worst on-treatment CTC grade compared to baseline CTC grade per subject: ALT, AST, alkaline phosphatase (ALP), total bilirubin and creatinine.

The analyses will be conducted using the 30-day safety window.

A by-subject listing of these laboratory parameters will be provided.

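### CBC and chemistry are scheduled every 2 weeks in Arm A but every 3 weeks in Arm C, and the SAP compares worst laboratory grade by arm with no allowance for the number of draws.

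*Protocol*

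**What the plan says.** **Schedules (Protocol Section 2).** Table 2-2 (Arm A) has "Each Cycle=2 wks", with "CBC w/differential at every cycle" and "Chemistry panel at every cycle (includes AST, ALT, total bilirubin". Table 2-4 (Arm C) has "Cycle 1 Each Cycle=6wks", with "CBC w/differential on Day 1 and Day 22 (+/- 3 days) of each cycle" and "Chemistry panel on Day 1 and Day 22 (+/- 3 days) of every cycle". The chemistry panel includes the liver tests, creatinine, glucose and the electrolytes.

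**Analysis.** SAP 7.1.2 sets the general rule: "subjects will be counted only once for each lab parameter according to their worst on treatment CTC grade". SAP 7.6.10.1 (hematology), 7.6.10.2 (serum chemistry) and 7.6.10.3 (electrolytes) apply it; in the words of 7.6.10.2, results are "summarized by treatment group as worst CTC grade on-treatment per subject". SAP 7.6.10.4 adds, by arm, the number of subjects with on-treatment ALT or AST above 3, 5, 10 and 20 times ULN, and related bilirubin and ALP counts. Protocol 10.3.2 also summarizes laboratory results by worst grade.

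**Adjustment.** None of these sections adjusts for how often subjects were sampled. The exposure-adjusted rates in SAP 7.1.1 and 7.6.9 apply to adverse events, and they correct for time at risk rather than for the number of looks.

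**The concern.** A worst-ever measure can only rise as more samples are taken. When two arms are sampled at different rates, a worst-grade table mixes the effect of the drugs with the effect of looking more often. Abnormalities that resolve between draws are missed more often in the arm with wider gaps.

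Laboratory abnormalities are named in the endpoint for the secondary safety objective (Protocol Table 4-1). A reader comparing the Arm A and Arm C columns for neutropenia, transaminases or electrolytes would take the difference as a drug effect, although part of it could come from the schedule.

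The other scheduled tests do not share the problem, which is specific to CBC and chemistry. Converted to weeks, amylase, lipase and thyroid tests fall at 0, 2, 6, 8, 12, 18 in Arm A and at 0, 3, 6, 9, 12, 18 in Arm C. ECGs fall at 0, 6, 12, 24, 36 in both arms, and urine protein every 6 weeks in both.

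**Working it through.** The plan states no figure on this point, so there is none to reproduce.

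**Inputs from the documents.** Arm A draws every 14 days (Table 2-2). Arm C draws on Days 1 and 22 of 42, so every 21 days (Table 2-4). Planned size is 319 per arm (Protocol 10.1).

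**Assumptions, because the documents give no durations or onset times.** Toxicity is equal in both arms, an episode lasts d days, onset is uniform relative to the draws, and only scheduled draws count.

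**Draws.** Per 42 days: 42/14 = 3 v 42/21 = 2, ratio 1.5. Per 12 weeks: 6 v 4.

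**Chance that one episode is caught.** min(1, d/14) in Arm A and min(1, d/21) in Arm C:

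| d (days) | Arm A | Arm C | Ratio |
|---|---|---|---|
| 3 | 21.4% | 14.3% | 1.50 |
| 7 | 50.0% | 33.3% | 1.50 |
| 14 | 100% | 66.7% | 1.50 |
| 16 | 100% | 76.2% | 1.31 |
| 18 | 100% | 85.7% | 1.17 |
| 21 or more | 100% | 100% | 1.00 |

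If the ±3-day window makes the Arm C gaps 18 and 24 days, its detection becomes [min(d,18) + min(d,24)]/42. The ratio stays at 1.50 up to 14 days and is 1.08 at 21 days.

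**Repeat episodes.** With k independent 7-day episodes, a subject is counted with probability 1 − (1 − p)^k, where p is 1/2 in Arm A and 1/3 in Arm C. The ratio is 1.50 for k = 1, 1.35 for 2, 1.24 for 3, 1.12 for 5 and 1.02 for 10.

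**Illustration.** Suppose 20% of subjects in each arm have one 7-day episode. Arm A shows 0.20 × 0.500 = 10.0% (about 32 of 319) and Arm C shows 0.20 × 0.333 = 6.7% (about 21 of 319).

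**If onset follows sunitinib dosing.** The Day 22 draw is in the fourth dosing week, and the next Day 1 draw follows 2 weeks off drug. The outcome for a 7-day episode in Arm C then depends on when it starts:
- Uniform over the 28 dosing days: caught 7/28 = 25% of the time, against 50% in Arm A (ratio 2.0).
- Starting on Days 16 to 22: always caught in Arm C, against 50% in Arm A, so the direction reverses.
- Starting after the Day 22 draw and ending before the next Day 1: never caught by a scheduled draw.

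**Check of the proposed measure.** One 7-day episode in 42 days gives an expected 3 × 7/42 = 0.50 abnormal draws of 3 in Arm A and 2 × 7/42 = 0.33 of 2 in Arm C. Both are 16.7%. Under random onset the expected percentage of abnormal draws does not depend on draw frequency, whatever the duration.

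**The case against.** The strongest reply is that neither the size nor the direction of the effect is established. The documents give no durations for Grade 3-4 laboratory findings, and those lasting 21 days or more are unaffected. Random onset is a doubtful assumption for a drug given 4 weeks on and 2 weeks off. Extra tests are allowed as clinically needed (notes to Tables 2-2 and 2-4), dose delays call for weekly or more frequent re-evaluation (Protocol 7.4.1), and delayed doses also delay the procedures. The tables are descriptive, with no laboratory hypothesis test. Findings that are clinically significant, interrupt treatment or need corrective therapy are also recorded as adverse events (Protocol 9.2.6). Under random onset, any bias counts against the experimental arm.

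All of this stands, and it limits the claim. A reader might infer that Arm A laboratory toxicity will be overstated by half, or that any excess in Arm A is an artifact of sampling. The documents support neither: 1.5 applies to a single short episode under random onset, and the actual mix of durations and timings is unknown.

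The reply does not remove the unequal sampling or supply an adjustment. Recording some abnormalities as adverse events does not help where the abnormality was never sampled.

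**Conclusion.** The point holds in limited form. CBC and chemistry are drawn 3 times per 6 weeks in Arm A and twice in Arm C, and the SAP compares the arms on measures that depend on the number of draws. With equal toxicity, random onset and scheduled draws only, a single abnormality of 14 days or less is detected 1.5 times as often in Arm A. The ratio declines to 1.0 at 21 days, and repeat episodes and unscheduled draws shrink it. If toxicity tracks the sunitinib cycle, it could be larger or reversed. What is affected is the reading of descriptive tables for a named secondary safety endpoint; PFS, OS and ORR are not touched. The thyroid counts in SAP 7.6.10.4 are also outside the point, because those tests are scheduled equally often in both arms.

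**What to change.** Keep the present worst-grade and threshold tables. For CBC, chemistry and electrolytes in SAP 7.6.10.1 to 7.6.10.3, and the hepatic part of 7.6.10.4, add for Arms A and C:

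- next to each count, the percentage of scheduled on-treatment draws at Grade 3-4 (or above the hepatic threshold);
- the number of scheduled draws per subject;
- a footnote that draws are 2-weekly in Arm A and 3-weekly in Arm C, and that the Arm C Day 1 draw from Cycle 2 on follows 2 weeks off drug.

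The percentage should use scheduled draws only, because follow-up tests in subjects already abnormal would inflate it.

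Matching the arms by keeping only Days 1 and 29 of each 6 weeks in Arm A is not recommended. It leaves gaps of 28 and 14 days, so detection is [min(d,28) + min(d,14)]/42. That gives 76% v 86% in Arm C at 18 days and 83% v 100% at 21 days, which reverses the bias.

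The cost is SAP wording and one extra set of columns from data already collected, with no change to the blood-draw schedule or to patient care. The percentage weights by how long an abnormality lasts, so it supplements the subject-level incidence and does not replace it.

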Tumor Assessments	First tumor assessment post-baseline should be performed Week 12 (± 7 days) following randomization. Use same imaging method as was used at baseline. Subsequent tumor assessments should occur at every 6 weeks (± 7 days) until Week 60, then every 12 weeks (± 14 days) until radiographic progression, assessed by the investigator and confirmed by the BICR.		CT/MRI of the chest, abdomen, pelvis, and all known sites of disease. Tumor assessments should be performed at the specified time points regardless of dosing delays. See Section 9.1 for additional details. Treatment Beyond Progression A radiographic assessment/ scan should be performed within 6 weeks of initial investigator-assessed progression. Refer to Section 8.1.4 for tumor assessment associated with Treatment beyond progression.
[REDACTED]			
[REDACTED]	■	■	[REDACTED]
[REDACTED]	■	■	[REDACTED]
[REDACTED]			
[REDACTED]	■		[REDACTED]
[REDACTED]	■	■	[REDACTED]

Table 2-2: On Treatment Procedural Outline for Arm A Nivolumab Combined with Cabozantinib, Doublet (CA2099ER)

Procedure	Cycle 1, Day 1 Cycle=2 wks	C2 and subsequent visits ^a Each Cycle=2 wks	Notes
Randomize	X		Begins with call to Interactive Response Technology (IRT). Participants must have an evaluable PD-L1 result from the central lab in order to be randomized.
Administer Nivolumab and Cabozantinib	X	X	See Section 7 . Dispense study treatment as appropriate. Day 1 Treatment must begin within 3 days (72 hours) of Randomization)

Abbreviations: C=cycle; D=day; wks= weeks. For abbreviations on lab tests refer back to [Section 9.4.1](#).

Notes: Some of the assessments referred to in this section may not be captured as data in the eCRF. They are intended to be used as safety monitoring by the treating physician. Additional testing or assessments may be performed as clinically necessary or where required by institutional or local regulations.

^a If a dose is delayed, the procedures scheduled for that same timepoint should also be delayed to coincide with when that timepoint's dosing actually occurs.

Table 2-3: On Treatment Procedural Outline for Arm B Nivolumab and Ipilimumab Combined with Cabozantinib, Triplet (CA2099ER)

CA2099ER Global Revised Protocol 01

Implementation of CA2099ER Global Revised Protocol 01 stops further randomization into Arm B. Participants previously randomized to Arm B continue with Arm B treatment and continue with Arm B clinical planned events, per protocol.

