Procedure	Part 1		Part 2	Notes (Please note differences in cycle durations between Part 1 and Part 2)
	Cycle 1 (Each Cycle=3 wks)	C2-C4 ^a (Each Cycle= 3 wks)	C5 and Subsequent visits ^a (Each Cycle=2 wks)	
Safety Assessments				
Targeted Physical Examination, Vital Signs, Performance Status	X	X	X	Weight, BP, HR, RR, temperature, and Karnofsky Performance Status (KPS) (Appendix 7). Performance Status to be performed within 72 hours prior to dosing.
Assessment of Signs and Symptoms	X	X	X	
Adverse Events and Serious Adverse Events Assessment	X	X	X	Record at each visit. Participants will be followed for drug-related toxicities until these toxicities resolve, return to baseline, or are deemed irreversible. All adverse events will be documented for a minimum of 100 days after last dose (Appendix 3).
[REDACTED]	[REDACTED]	[REDACTED]	[REDACTED]	[REDACTED]
Electrocardiogram (ECG)	X	X (See notes)	X (See notes)	Fridericia corrected QT (QTcF) required. Only Cycles 1, 3, 5, then every 6 cycles (ie, Cycles 11, 17, 23, etc). If any time there is an increase in QTcF interval to an absolute value > 500 msec, 2 additional ECGs must be performed each with intervals approximately 3 minutes apart.
Laboratory Tests (includes blood and urine samples)	X	X	X (See notes)	See Section 9.4.1 for additional details on tests required. Laboratory tests do not need to be repeated at C1D1 if performed within 14 days prior to first dose. After C1D1, within 72 hours prior to dosing. 
 CBC w/differential at every cycle

Table 2-3: On Treatment Procedural Outline for Arm B Nivolumab and Ipilimumab Combined with Cabozantinib, Triplet (CA2099ER)

CA2099ER Global Revised Protocol 01

Implementation of CA2099ER Global Revised Protocol 01 stops further randomization into Arm B. Participants previously randomized to Arm B continue with Arm B treatment and continue with Arm B clinical planned events, per protocol.

Procedure	Part 1		Part 2	Notes (Please note differences in cycle durations between Part 1 and Part 2)
	Cycle 1 (Each Cycle=3 wks)	C2-C4 ^a (Each Cycle= 3 wks)	C5 and Subsequent visits ^a (Each Cycle=2 wks)	

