Abbreviations: IV=intravenous; PO= by mouth; QD= once daily

Note: Implementation of CA2099ER Global Revised Protocol 01 stops further randomization into Arm B. Participants previously randomized to Arm B continue with Arm B treatment and continue with Arm B clinically planned events, per protocol

Participants should begin study treatment within 3 days (72 hours) of randomization.

For **Arm A**, participants should receive nivolumab at a dose of 240 mg as an approximately 30 minute infusion on Day 1 of each treatment cycle until progression, unacceptable toxicity, withdrawal of consent, completion of 24 months of treatment (from the first dose on Cycle 1), or the end of the study, whichever occurs first. The first cabozantinib dose should be given in the evening on Day 1, Cycle 1 (after the Cycle 1 nivolumab dose).

For **Arm B (Note: only applicable to participants who randomized to Arm B prior to Revised Protocol 01)**, when nivolumab and ipilimumab are to be administered on the same day, nivolumab is to be administered first. Nivolumab infusion (approximately 30 minutes) must be promptly followed by a flush of diluent to clear the line of nivolumab before starting the ipilimumab infusion. The second infusion will always be the ipilimumab study drug (approximately 30 minutes infusion) and will start after the infusion line has been flushed, filters changed and participant has been observed to ensure no infusion reaction has occurred. The time in between infusions is expected to be at least 30 minutes (from the end of the nivolumab infusion to the start of the ipilimumab infusion). The first cabozantinib dose should be given in the evening on Day 1, Cycle 1 (after the Cycle 1 nivolumab and ipilimumab doses).

Starting with Cycle 5 in Arm B, participants should receive nivolumab at a dose of 240 mg as a 30 minute infusion on Day 1 of each treatment cycle until progression, unacceptable toxicity, withdrawal of consent, completion of 24 months of treatment (from the first dose on Cycle 1), or the end of the study, whichever occurs first.

Dosing calculations for nivolumab and ipilimumab should be based on the body weight assessed at baseline. It is not necessary to re-calculate subsequent doses if the participant weight is within 10% of the weight used to calculate the previous dose. All doses should be rounded up or to the nearest milligram per institutional standard.

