There will be no dose escalations or reductions of nivolumab or ipilimumab allowed. Participants may be dosed with nivolumab no less than 12 days from the previous dose during q2w cycles.

Participants may be dosed with nivolumab and ipilimumab no less than 19 days from the previous dose during q3w cycles (ie, Cycles 1-4 in Arm B). Participants in Arm B may be dosed with the first nivolumab maintenance dose (Cycle 5) no less than 19 days from the previous nivolumab and ipilimumab doses. Premedications are not recommended for the first dose of nivolumab or ipilimumab.

Participants should be carefully monitored for infusion reactions during nivolumab and/or ipilimumab administration. If an acute infusion reaction is noted, participants should be managed according to [Section 7.4.4](#).

Doses of nivolumab and/or ipilimumab may be interrupted, delayed, or discontinued depending on how well the participant tolerates the treatment. Dosing visits are not skipped, only delayed. The only exception is Cycle 4 in Arm B, which may be skipped (omitted) only for the reasons specified in [Section 7.4.3.1](#) and [Section 8.1.1](#) below.

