7.4.1 Dose Delay Criteria

Dose delay criteria for management of adverse events during nivolumab, ipilimumab, cabozantinib, or sunitinib treatment are outlined in this section.

Dosing of nivolumab (in Arm A) or nivolumab and ipilimumab (in Arm B) may be delayed without delay of cabozantinib dosing if toxicity is felt to be related to only nivolumab (Arm A) or nivolumab and ipilimumab (Arm B) and not related to cabozantinib. Conversely, dosing of cabozantinib may be delayed without delay of nivolumab dosing (in Arm A) or nivolumab and ipilimumab dosing (in Arm B) if toxicity is felt to be related to only cabozantinib and not related to nivolumab (Arm A) or nivolumab and ipilimumab (Arm B). However, if toxicity is considered related to all study drugs or if the investigator is unable to determine which study drug is the cause of the AE, then all study drugs in the combination should be delayed.

Participants who require dose delay should be re-evaluated weekly or more frequently if clinically indicated and resume dosing when re-treatment criteria are met (see Section 7.4.3).

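### Table 2-2 footnote a does not say what happens to urine protein and ECG when only nivolumab is held, so both can slip by up to 4 weeks while cabozantinib continues

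*Protocol*

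**What the plan says.** Five parts of the Protocol bear on this.

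- **Table 2-2, footnote a (Arm A), repeated under Table 2-3 (Arm B).** "If a dose is delayed, the procedures scheduled for that same timepoint should also be delayed to coincide with when" the dosing takes place. No drug is named and no exception is given.
- **Section 7.4.1.** Nivolumab "may be delayed without delay of cabozantinib dosing if toxicity is felt to be related to only nivolumab". If attribution is unclear, or the toxicity is ascribed to all study drugs, all of them are held. Participants under a delay are re-evaluated at least weekly; the tests to be done are not listed.
- **Section 7.1.** In Arm A, "participants should receive nivolumab at a dose of 240 mg as an approximately 30 minute infusion on Day 1 of each treatment cycle". Of nivolumab and ipilimumab it adds: "Dosing visits are not skipped, only delayed".
- **Table 2-2, laboratory and ECG rows.** "Urine protein and urine creatinine (for UPCR, preferred) or urine dipstick for protein every 3 cycles". ECG is done at Cycles 1, 4 and 7 and then every sixth cycle. By contrast, tumor assessments are expressly kept on schedule whatever happens to dosing, and pregnancy tests run every 4 weeks.
- **Section 7.4.1.2.** Cabozantinib must be held for a UPCR above 2.0 (or the dipstick or 24-hour equivalent) and for a confirmed QTcF above 500 msec.

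Section 8.1.1 adds that a nivolumab delay of more than 6 weeks from the previous dose requires discontinuation, with exceptions, including prolonged steroid tapers. During such longer delays, safety visits and laboratory studies continue every 6 weeks.

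**The concern.** Footnote a suits a single-drug arm. Under Table 2-4, when sunitinib is held, exposure and monitoring pause together. In Arm A the two can separate: nivolumab is held, the cycle count stops, and the participant goes on taking cabozantinib daily. Two of the tests tied to the cycle count are those that detect proteinuria and QTc prolongation, each of which has its own cabozantinib hold rule. Either can be present without symptoms, so the scheduled test is the main way to find it. A site that follows the footnote as written could postpone both tests during continuing exposure and be within the protocol.

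**Working it through.** The plan gives no figure for these intervals under a hold, so there is none to reproduce. The check is calendar arithmetic.

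**Inputs**
- Arm A cycle length: 2 weeks (Table 2-2).
- Urine protein: Cycles 1, 4, 7, 10 and so on. ECG: Cycles 1, 4, 7, 13, 19, 25 and so on (Table 2-2).
- Ordinary limit: 6 weeks from the previous nivolumab dose (Section 8.1.1).
- Cabozantinib: one dose a day, continued during the hold (Sections 7.1 and 7.4.1).

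**Nominal calendar.** Cycle 1 = week 0, Cycle 4 = week 6, Cycle 7 = week 12, Cycle 10 = week 18, Cycle 13 = week 24.
- Urine protein: 3 × 2 = 6 weeks.
- ECG: 3 × 2 = 6 weeks up to Cycle 7, then 6 × 2 = 12 weeks.

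**Slip.** Delay = gap from previous dose − 2 weeks. At the ordinary limit this is 6 − 2 = 4 weeks. Stretched interval = nominal interval + delay.

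| Delay (weeks) | Urine protein (nominal 6) | ECG to Cycle 7 (nominal 6) | ECG after Cycle 7 (nominal 12) |
|---|---|---|---|
| 1 | 7 | 7 | 13 |
| 2 | 8 | 8 | 14 |
| 4 (ordinary limit) | 10 | 10 | 16 |

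At the limit, the daily cabozantinib doses between tests rise from 6 × 7 = 42 to 10 × 7 = 70, or from 12 × 7 = 84 to 16 × 7 = 112.

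**Two examples**
- *Held cycle is a test cycle.* Cycle 3 is given at week 4; Cycle 4 is due at week 6 and given at week 10. If the tests wait for the dose, they run from week 0 to week 10. If they were done at week 6 and repeated at week 10, no interval is stretched. If they were done at week 6 and counted as the Cycle 4 tests, the next are at Cycle 7, in week 10 + 6 = 16, which is again 10 weeks.
- *Held cycle is not a test cycle.* Cycle 7 is given at week 12; Cycle 8 is due at week 14 and given at week 18. Urine protein at Cycle 10 falls at 18 + 4 = week 22, 10 weeks after Cycle 7. ECG at Cycle 13 falls at 18 + 10 = week 28, 16 weeks after Cycle 7.

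**Arm B from Cycle 5.** Cycles 1, 3 and 5 fall at weeks 0, 6 and 12. After that urine protein is every 3 × 2 = 6 weeks and ECG every 6 × 2 = 12 weeks. The same 4-week slip gives 10 and 16 weeks.

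**Longer holds.** For delays above 6 weeks, the 6-weekly laboratory studies in Section 8.1.1 match the nominal urine protein interval. They plausibly include it, since Table 2-2 and Section 9.4.1 count urine among the laboratory tests. ECG is not a laboratory test and is not named there.

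**The case against.** The strongest objection is that footnote a can be read drug by drug. Table 2-4 applies the same footnote to sunitinib, a daily oral drug, and gives it specified dosing days. Table 2-2 has a joint administration row for nivolumab and cabozantinib at every cycle. Cabozantinib may also continue alone after nivolumab stops, so the cycle-numbered tests must be schedulable without a nivolumab dose. On that view, if cabozantinib is taken on time, the timepoint has not moved. This stands as a possible reading, and it is why the point is one of unsettled wording and not of a rule that clearly displaces the tests. It does not remove the point, because the footnote does not choose between the readings and they give different safety schedules.

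Second, participants are seen. Weekly re-evaluation applies to any hold, extra tests may be done when clinically necessary, and unclear attribution means cabozantinib is held too. All of this stands. But Section 7.4.1 names no tests, and permission to test is not a schedule. Because it names none, confining the point to urine protein and ECG is a judgement: each has its own cabozantinib hold rule and is easily left out of a review prompted by another toxicity.

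Third, 4 weeks is the ordinary upper limit; shorter delays cost correspondingly less. The documents give no frequency for nivolumab-only holds and no evidence that 10-week or 16-week spacing is unsafe, and the protocol already accepts 12 weeks between ECGs. This also stands.

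A reader might infer that safety monitoring lapses altogether during a hold. The weekly re-evaluation rules that out. A reader might also carry the point into Arm B's 3-week cycles. Revised Protocol 01 (18-Dec-2017) stopped randomization to Arm B, the letter on site timing is dated 08-Feb-2018, this version is dated 03-May-2019, and four 3-week cycles take 12 weeks. Unless a site implemented the change about a year late, nobody remains in those cycles.

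**Conclusion.** The point holds as a gap in the wording, worth considering and cheap to close. On its plain reading, footnote a lets urine protein and ECG move with a held nivolumab visit while cabozantinib continues. One interval is stretched by the length of the delay, at most 4 weeks for an ordinary hold: urine protein 6 to 10 weeks, ECG 6 to 10 weeks up to Cycle 7 or 12 to 16 weeks afterwards. The firm gap is urine protein during holds of up to 6 weeks, and ECG during holds of any length.

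The 4-week figure assumes that the 6-week limit runs from the previous dose, as Section 8.1.1 says. Section 7.4.3.1 could be read as counting from the missed date. The slip would then be 6 weeks, giving urine protein 6 + 6 = 12 weeks and ECG 12 or 18 weeks. Confidence is medium: one safety row of Table 2-2 is redacted, and the Appendix 5 algorithms and the cabozantinib brochure were not available, so an instruction may exist there.

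This is a participant-safety matter only. A reader might look for an effect on PFS or OS; there is none, because tumor assessments are protected from dosing delays and survival follow-up does not depend on the cycle count.

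**What to change.** Add to footnote a in Tables 2-2 and 2-3:

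*If only nivolumab is held and cabozantinib continues, urine protein and ECG stay on the calendar weeks they would have had with on-time dosing (urine protein every 6 weeks; ECG at weeks 6 and 12, then every 12 weeks in Arm A; the equivalent weeks in Arm B). Each is done at the last study visit of any kind (dosing or re-evaluation) on or before that date, and replaces the corresponding cycle-numbered test.*

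Allowing any study visit matters, because when the held cycle is not a test cycle the due date can fall after the hold has ended, when there is no re-evaluation visit. Applied to the two examples:
- *Cycle 4 delayed from week 6 to week 10:* both tests are done at the week 6 visit and again at the week 12 dosing visit, so intervals stay at 6 weeks. If Cycle 4 is given at week 9, the second tests fall at week 11, an interval of 5 weeks.
- *Cycle 8 delayed from week 14 to week 18:* urine protein is done at week 18 (the Cycle 8 visit). ECG is done at week 24 (the Cycle 11 visit, 18 + 3 × 2), 12 weeks after Cycle 7.

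The cost is one footnote addition in two tables and, per hold, an occasional off-grid or extra urine test and ECG. No new visit type is needed.
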